8.3.5 Near-infrared spectroscopy

The cerebral hemoglobin oxygenation will be assessed by near-infrared spectroscopy of cerebral tissue via one or two sensors placed on the skin overlying the skull. Cerebral oxygenation will be recorded for 30 minutes (range 15-60 minutes) on each study day per schedule in Appendix A. Average saturation as well as the amplitude and frequency of oscillations in tissue oxygenation will be analyzed.

Skeletal muscle reperfusion dynamics will be assessed by measuring the changes in muscle hemoglobin oxygenation by near-infrared spectroscopy after inflation and deflation of an occlusive thigh cuff on each study day per schedule in Appendix A. The skeletal muscle recording will last approximately 30 minutes and includes a 3-minute inflation of a pneumatic cuff on the lower limb.

8.3.6 Heart rate variability

When patients are admitted or transferred to the PICU, they are connected to bedside monitoring which includes electrocardiogram (EKG), respiration waveforms, oxygen levels, and blood pressures. The ICU monitors display instantaneous values for these clinical parameters and plots of their trends. These waveforms will be archived, compressed and uploaded for offline analysis of patterns of heart rate variability and integration of results with the clinical course. A 60 minute reading will be taken in the supine position. Readings will undertaken every six hours for the first 24 hours of admission, then daily until the patient's Blantyre Coma Score is ≥ 3 , and again upon discharge. The aim is to undertake the recordings at the same time every day; currently 0600, 1200, 1800 and 0000. Readings will be discontinued upon death or improvement of Blantyre coma score to ≥ 3 .

8.3.7 Heart and lung ultrasound

A protocolized heart and lung ultrasound (HLUS) examination will be performed within 4 hours of admission. All sonographic images will be acquired with a Butterfly iQ (USA) phased array transducer using transverse view. Each HLUS will be performed by the same trained investigator. Based on the international evidence-based recommendations for POCUS of the lungs, a complete eight-zone examination will be used. The anterior and lateral chest wall will be divided and imaging obtained bilaterally in a parallel plane. Each zone will be scored based on the most agreed upon scoring system for LUS which uses four ultrasound aeration patterns:

1. Normal = the presence of lung sliding with A-lines or fewer than two isolated B-lines, scored as 0
2. Moderate loss of lung aeration = multiple well-defined B-lines (B1-lines) present, scored as 1
3. Severe loss of lung aeration = the presence of multiple coalescent B-lines (B2-lines), scored as 2
4. Lung consolidation = tissue pattern characterized by dynamic air bronchograms, scored as 3.

The worst ultrasound pattern observed in each zone will be recorded and used to calculate the sum of the scores with a maximum total score of 24. Each child's lung ultrasound will be repeated and scored daily until discharge, death, normalization, or day 4 of admission, whichever comes first.

The cardiac function will be evaluated using a non-invasive cardiac output monitor (USCOM, Australia). The ultrasound probe will be placed on the suprasternal notch and the blood flow will be captured. The machine performs calculations and reports cardiac output, cardiac index, stroke volume, stroke volume index, systemic vascular resistance, and stroke volume variability. Each child's cardiac ultrasound will be repeated, and results recorded daily until discharge, death, normalization, or day 4 of admission, whichever comes first.

8.4 Specimen Preparation, Handling, and Shipping

8.4.1 Instructions for Specimen Preparation, Handling, and Storage

Admission CSF, urine and plasma samples from each participant will be archived. The one ml blood sample dedicated for plasma archive will be aliquoted into a cryovial for long term storage in a -80°C freezer. One ml of CSF will immediately be transferred to a cryovial prior to distributing the remainder of the sample for culture and cytology. Urine will be collected in the process of inserting a Foley catheter or via a sterile bag affixed to the patient and transferred to a cryovial.

Cryovials for plasma, urine and CSF will be identified with a unique bar code and the location in the freezer recorded with dedicated sample tracking software. Thick and thin blood smears to evaluate the presence of malaria parasitemia will also be stored past the conclusion of the study. They will be labeled with a unique bar code and stored in a slide file cabinet in a locked storeroom adjacent to the PRW as detailed in Section 14.7.

Detailed protocols for both procedures are included in the study's Manual of Operating Procedures (MOP).

8.4.2 Specimen Shipment

Samples will be shipped in accordance with IATA requirements and with any required Materials Transfer Agreements in place.

9 ASSESSMENT OF SAFETY

9.1 Specification of Safety Parameters

The primary safety parameter for this study is a comparison of survival of the participants in the three treatment arms. In addition, we will be assessing long term neurological sequelae for all participants.

9.2 Methods and Timing for Assessing, Recording, and Analyzing Safety Parameters

9.2.1 Adverse Events

ICH E6 defines an adverse event (AE) as any untoward medical occurrence in a participant or clinical investigation subject exposed to an intervention or a pharmaceutical product regardless of its causal relationship to the study treatment. An AE can therefore be any unfavorable and unintended sign (including an abnormal laboratory finding), symptom, or disease, temporally associated with the use of a medicinal (investigational) product. The occurrence of an AE may come to the attention of study personnel during study visits and interviews of a study participant presenting for medical care, or upon review by a study monitor.

Because the safety profiles of the two study interventions are fairly well-defined, and the patient population is critically ill, only AE considered to be possibly attributed to the study intervention will be collected. These will include AE known to be related to the study interventions and pre-specified in 2.4.1.2 and any other unanticipated AE that in the opinion of the investigator was attributed to study interventions. All AEs occurring while on study will be documented appropriately regardless of relationship. All AEs will be followed to adequate resolution.

Any medical condition present at the time that the participant is screened should be considered as baseline and not reported as an AE. However, if the medical condition deteriorates at any time during the study, it will be recorded as an AE.

All AEs will be graded for severity and relationship to study interventions.

Since mortality is an endpoint, death will not routinely be considered an Adverse Event for study purposes. Only events meeting leading to death, hospitalization or prolongation of hospitalization that are outlined in section 2.4.1.2, or that were unanticipated, but that are considered to be possibly related to the study intervention will be reported as SAE.

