3 OBJECTIVES

3.1 Study Objectives

Primary Objective

Compare final outcomes in pediatric CM patients receiving usual care (Arm 3) with both of two interventions (Arm 1 and Arm 2).

Secondary Objectives:

1. Among survivors of this interventional study, compare rates of adverse neurological outcomes in those assigned to the two interventions and those assigned to usual care.
2. Among all children admitted to the PRW with CM whose parents consent to screening, evaluate and validate biomarkers of increased brain volume.
3. Assess the safety of early intubation and mechanical ventilation as well as intravenous hypertonic saline in children with CM.
4. Establish association between specific pathogenic mechanisms and TCD-derived phenotypes.
 - a. microvascular obstruction phenotype with MRI findings
 - b. hyperemia phenotype with hypercapnia on blood gas analysis, acidosis, and seizures on EEG
 - c. vasospasm phenotype with regional EEG findings of loss of fast frequencies and increased slow frequencies in territories of affected vessels and MRI findings with localized ischemic changes
 - d. low flow phenotype with compromised hemodynamics, diminished compensatory reserve and increased brain volume per MRI

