9.2.1.3 Expected Adverse Events

All adverse events meeting the criteria listed above will be collected. Special concern will be paid to the following adverse events as they are known side effect of the investigational drugs:

- Potentially attributable to the hypertonic saline intervention:
 - Hypernatremia
 - Hypokalemia
 - Hyperkalemia
 - Phlebitis
- Potentially attributable to the intubation intervention:
 - Pneumothorax
 - Pneumomediastinum
 - Subglottic stenosis
 - Stridor
 - Tracheostomy
 - Bronchospasm
 - Pulmonary hemorrhage

- Respiratory nosocomial infections
- Hypotension
- Endotracheal tube obstruction
- Inadvertent endotracheal tube dislodgment
- Bradycardia induced by vagal response

Adverse Event grading tables (attached as Appendix B) will be used to define these conditions. These events will be captured in the CRF and subsequently in tabular format, listing time of event onset, time of event resolution, brief description of the event, clinician's assessment of severity, and clinician's assessment of relation to the intervention. They will be reported to the local ISM on a monthly basis, and an annual report of these events will be presented to the DSMB, as well as both IRBs. The events will be captured for the duration of the participants' stay on the PICU/PRW, independent of whether the participant is still receiving interventional therapy.

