9.2.3 Serious Adverse Events

An adverse event or suspected adverse reaction is considered "serious" if, in the view of either the investigator or sponsor, it results in any of the following outcomes:

- Death,
- A life-threatening adverse event,
- Hospitalization or prolongation of existing hospitalization,
- A persistent or significant incapacity or substantial disruption of the ability to conduct normal life functions, or
- A congenital anomaly/birth defect.

Important medical events that may not result in death, be life-threatening, or require hospitalizations may be considered serious when, based upon appropriate medical judgment they may jeopardize the participant and may require medical or surgical intervention to prevent one of the outcomes listed in this definition. Only events that are not attributable to the malarial illness, that are outlined in section 2.4.1.2, or that were unanticipated, but that are considered to be possibly related to the study intervention will be graded and reported as Adverse Events to the sponsor, IRBs, and independent safety monitors.

- Life-threatening adverse event: An adverse event is considered “life-threatening” if, in the view of either the investigator or sponsor, its occurrence places the participant or subject at immediate risk of death. It does not include an adverse event, had it occurred in a more severe form, might have caused death.

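### Sections 9.2.1 and 9.2.3 give conflicting rules on which adverse events are collected and graded; under the attribution-only rule, adverse-event rates by arm could not be interpreted

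*Combined protocol and SAP*

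**What the plan says.** Section 9.2.1 first restricts collection, on the ground that both interventions are well characterised and the children are critically ill: "only AE considered to be possibly attributed to the study intervention will be collected". It names two classes that qualify: known events pre-specified in Section 2.4.1.2, and unanticipated events that the investigator attributes to the intervention. The next sentence says: "All AEs occurring while on study will be documented appropriately regardless of relationship". The section then adds: "All AEs will be graded for severity and relationship to study interventions".

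Section 9.2.3 takes the narrower line. It limits the handling of events to a selected set "that are considered to be possibly related to the study intervention will be graded and reported as Adverse Events".

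Section 9.2.1.3 points back to Section 9.2.1: "All adverse events meeting the criteria listed above will be collected". It lists events for both interventions, sets the capture window as the whole PICU/PRW stay, and includes the clinician's view of relatedness among the recorded items.

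On the use of safety data, Secondary Objective 3 in Section 3.1 is: "Assess the safety of early intubation and mechanical ventilation as well as intravenous hypertonic saline in children with CM". Section 9.1 says: "The primary safety parameter for this study is a comparison of survival of the participants in the three treatment arms". It continues: "In addition, we will be assessing long term neurological sequelae for all participants".

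**The concern.** Nothing in the documents defines collecting an event as different from documenting it, so two data managers could build different adverse-event datasets from Section 9.2.1. The choice matters because treatment is unmasked (Section 5.3.2) and a study clinician judges relatedness partly from the timing of the event relative to the interventions (Section 9.2.1.2). A UC child who is never ventilated has no study intervention to which an event can be attributed. Under the attribution-only rule, a nosocomial infection or a fall in blood pressure in that child stays out of the data, while the same event in the ventilation (VENT) or hypertonic saline (HPS) arm can enter.

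Two uses of the data need a background rate. Section 4 extends the ventilation-safety objective to screened children who are not randomized; they receive no trial intervention and are informative only if events are recorded without an attribution test. Section 9.6 has the DSMB assess safety by arm and look for a raised rate of serious unexpected reactions, and a raised rate needs a reference.

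**Working it through.** The plan states no adverse-event rate and no sample size based on adverse events, so there is no figure of its own to reproduce. The check is textual, followed by an illustration on assumed rates.

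**1. The text side by side**

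| Step | Restrictive statement | Inclusive statement |
|---|---|---|
| Collect | 9.2.1: only events possibly attributed to the intervention | 9.2.1: all on-study events documented, whatever the relationship |
| Grade | 9.2.3: only the selected, possibly related events | 9.2.1: all events, for severity and relationship |
| Listed events | 9.2.1.3: those that meet the criteria of 9.2.1 | 9.2.1.3: relatedness is recorded for each event, which suggests that unrelated ones are captured too |

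The cross-reference adds to the problem. Section 2.4.1.2 lists hypertonic saline effects only; the ventilation risks are in Section 2.4.1.3.

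**2. Who can supply a UC rate**

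- UC total in Section 11.5: 16 randomized + 48 historical = 64. The historical share is 48/64 = 75%.
- Projected UC total in Section 4: 64 + 0 (2022) + 4 (2023) = 68. Randomized UC: 68 − 48 = 20.
- The historical controls come from an earlier observational study (2014–2017), so only 16 to 20 UC children can have events recorded under this protocol.

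**3. Illustration of the ascertainment effect**

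From the plan: HPS n = 32 (Section 11.7) and UC n = 16 or 20. Assumed: the same true event rate r in both arms, a share a of HPS events judged attributable, and no UC events captured.

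With 0/20 in UC, the smallest HPS count that gives p ≤ 0.05 in a two-sided Fisher test is 7/32:

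p = [C(32,7) + C(20,7) + 32 × C(20,6)] / C(52,7) = (3,365,856 + 77,520 + 1,240,320) / 133,784,560 = 0.035.

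With 0/16 in UC the threshold is 8/32 (p = 0.039). The chance of a spurious difference is therefore P(X ≥ 7) or P(X ≥ 8), with X ~ Binomial(32, r × a):

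| True rate r, both arms | UC n | a = 50% | a = 75% | a = 100% | All events collected in both arms |
|---|---|---|---|---|---|
| 10% | 20 | 0.1% | 0.8% | 3.6% | 1.7% |
| 20% | 20 | 3.6% | 19.5% | 46.5% | 3.1% |
| 30% | 20 | 19.5% | 60.2% | 88.7% | 3.3% |
| 50% | 20 | 72.2% | 98.1% | 100.0% | 4.6% |
| 30% | 16 | 9.6% | 43.4% | 78.8% | 3.1% |

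If UC captures 10% of its events instead of none, with r = 30%, a = 100% and n = 20, the figure is 66.7%.

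**4. Which listed events could be compared**

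- *Can occur and be observed without the intervention:* respiratory nosocomial infection, hypotension and bradycardia, for example. Section 4 sets two-hourly vital signs on both the PRW and the PICU. Appendix B, however, grades hypotension and bradycardia against pre-intubation values, which a never-intubated child does not have.
- *Electrolyte events:* the scheduled series is specified for HPS (Sections 4 and 8.2.1), so they are not comparable with UC under either rule.
- *Tube obstruction and dislodgment:* impossible without a tube.

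**The case against.** The best defence is that little in the planned analysis depends on this wording. Section 9.1 makes survival the primary safety parameter and adds neurological sequelae; both are captured as outcomes under either rule. Secondary Objective 3 does not itself name a comparison with UC. Section 11 plans no test of overall adverse-event rates between arms; the only event of this kind in Table 8 is hypotension shortly after sedation, start of ventilation or a pressure change. All of this stands. A reader might infer from the contradiction that the trial's safety comparison as a whole fails; the documents do not support that.

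Nor do they show that UC would have no events. Arms 2 and 3 can receive rescue ventilation (Section 11.1), which can produce attributable events in UC. A reader might also take the hospital-acquired infections in 20 of 61 children in the ventilated cohort cited in Section 2.2.2.1 as a measure of the bias. That is an external retrospective cohort of intubated children and does not measure bias in this trial.

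It can also be argued that Section 9.2.1 subjects only unanticipated events to the investigator's opinion and admits listed events by type, as the relatedness item in Section 9.2.1.3 suggests. This is a reasonable reading, but the text does not state it, and the list cited leaves out ventilation. It is a reason to write the rule down.

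Finally, new wording reaches few UC children: 0 projected in 2022 and 4 in 2023. That stands too, and is why the rule already applied must be disclosed.

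**Conclusion.** The contradiction is certain: two incompatible collection rules in one paragraph, repeated for grading and reporting in Section 9.2.3, with a cross-reference that covers only one of the two interventions. If the attribution-only rule is followed, recording depends on arm and on unmasked judgement, and adverse-event rates by arm cannot be interpreted under Secondary Objective 3 or in DSMB review.

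The size cannot be derived from the plan. The illustration gives anything from 0.1% to nearly 100% spurious differences, according to the assumed event rate, attribution share and UC capture, for a test that the plan does not specify. It shows that the effect is negligible for rare events and large for common ones. It does not predict what this trial will find.

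No stated sample size, power or alpha is affected, and the survival and neurological-sequelae comparisons stand. This should be corrected, but it does not threaten the primary result.

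**What to change.** - Delete the attribution-only collection sentence and reconcile Sections 9.2.1, 9.2.1.3 and 9.2.3 into one rule for collecting, grading and reporting.
- In all randomized arms, record the Section 9.2.1.3 events that can occur and be observed without the intervention, over the PICU/PRW stay already set there and regardless of judged relationship. Keep relatedness as the separate item that Section 9.2.1.3 already provides.
- For hypotension and bradycardia, use a baseline that also exists in non-intubated children. An enrolment value is one option; Section 4 already uses enrolment systolic pressure for its hypotension outcome.
- Extend the cross-reference to Section 2.4.1.3.
- Plan descriptive summaries of these events by arm. State that electrolyte and tube-specific events are not comparable with UC, and that historical controls contribute no adverse-event data under this protocol.
- Say whether the screened, non-randomized children named in Section 4 fall under the same rule.
- Disclose which rule was applied to children already randomized.

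The cost is modest: some extra CRF entry, and abstraction from source records for the 16 UC children already enrolled. If the attribution-only rule was used, equal treatment of the arms would call for the same abstraction in the 19 VENT and 3 HPS children that the Section 4 table shows through 2021. No extra blood sampling is needed, because electrolyte events are left out of the comparison with UC.

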9.2.1.1 Severity

For electrolyte abnormalities, toxicity tables (Appendix B) will be used. For other, non-protocol specific AEs the following grading system will be used:

- Mild: events require minimal or no treatment and do not interfere with the participant's daily activities.
- Moderate: events result in a low level of inconvenience or concern with the therapeutic measures. Moderate events may cause some interference with functioning.
- Severe: events interrupt a participant's usual daily activity and may require systemic drug therapy or other treatment. Severe events are usually incapacitating.
- Life threatening: any adverse drug experience that places the participant or subject, in the view of the investigator, at immediate risk of death from the reaction as it occurred, i.e., it does not include a reaction that had it occurred in a more severe form, might have caused death.

Changes in the severity of an AE will be documented to allow an assessment of the duration of the event at each level of intensity to be performed. Onset and duration of each episode of intermittent adverse events will be documented.

9.2.1.2 Relatedness

The relatedness of the AE will be assessed by a study clinician based on the temporal relationship of the AE and any interventions, as well as the likelihood of other causal etiologies of the specific AE.

Related – There is a reasonable possibility that the intervention caused the adverse event. Reasonable possibility means that there is evidence to suggest a causal relationship between the study product and the adverse event.

Not Related – There is not a reasonable possibility that the administration of the study product caused the event.

9.2.1.3 Expected Adverse Events

All adverse events meeting the criteria listed above will be collected. Special concern will be paid to the following adverse events as they are known side effect of the investigational drugs:

- Potentially attributable to the hypertonic saline intervention:
 - Hypernatremia
 - Hypokalemia
 - Hyperkalemia
 - Phlebitis
- Potentially attributable to the intubation intervention:
 - Pneumothorax
 - Pneumomediastinum
 - Subglottic stenosis
 - Stridor
 - Tracheostomy
 - Bronchospasm
 - Pulmonary hemorrhage

- Respiratory nosocomial infections
- Hypotension
- Endotracheal tube obstruction
- Inadvertent endotracheal tube dislodgment
- Bradycardia induced by vagal response

Adverse Event grading tables (attached as Appendix B) will be used to define these conditions. These events will be captured in the CRF and subsequently in tabular format, listing time of event onset, time of event resolution, brief description of the event, clinician's assessment of severity, and clinician's assessment of relation to the intervention. They will be reported to the local ISM on a monthly basis, and an annual report of these events will be presented to the DSMB, as well as both IRBs. The events will be captured for the duration of the participants' stay on the PICU/PRW, independent of whether the participant is still receiving interventional therapy.

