Side-effects: A theoretical danger of hypertonic saline administration is that rapid increases in sodium concentration may induce central pontine myelinolysis. This devastating neurological abnormality is a rare consequence of overly rapid correction of chronic hyponatremia. To date, there are no reports of central pontine myelinolysis occurring in participants receiving hypertonic saline for the treatment of increased ICP ^{139, 155, 156}. Additionally, there are no data clearly linking the use of hypertonic saline to the development of acute renal failure or to rebound increases in ICP in humans ^{85, 117, 119}.

The hypernatremia induced by hypertonic saline has been associated with coagulopathies and excessive intravascular volume ^{85, 119}. Electrolyte abnormalities (hyperchloremic metabolic acidosis and hypokalemia) can develop, necessitating careful monitoring ^{85, 118, 119}.

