2.4.1.2 Hypertonic saline

The known side-effects of hypertonic saline include:

- Hypernatremia
- Hypokalemia
- Rebound cerebral edema upon termination of therapy

These conditions are all a direct result of the increased sodium and osmolarity that are also the goal of the intervention. Assiduous monitoring of electrolytes (as described in 9.2.4) will therefore be undertaken to balance desired effects with possible side effects.

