9.2.3.1 Protocol defined SAEs

CM is a disease with a high mortality rate. Reported mortality rates range from 15 – 30%, with our site having a rate of 18% over the past 25 years. We anticipate the mortality rate in randomization arm 3 will be approximately 37%. All deaths not attributable to the malarial illness will be reported to independent safety monitors, IRBs, and the sponsor as required.

- Death not caused by respiratory arrest secondary to intracranial hypertension.
- Prolongation of existing hospitalization for more than 7 days due to an intervention.
- A life-threatening adverse event that is not part of the study outcomes defined in the study objectives, an attributable to an intervention.

9.2.4 Procedures to be Followed in the Event of Abnormal Laboratory Test Values or Abnormal Clinical Findings

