Appendix B - Adverse Event Table

Event	Grade 1	Grade 2	Grade 3	Grade 4
Hypernatremia	166-170 mEq/L	171-180 mEq/L	181-190 mEq/L	>191 mEq/L
Hyperkalemia	5.4-5.9mEq/L	6.0-6.4mEq/L	6.5-7.0mEq/L	> 7.0 mEq/L
Hypokalemia			2.0-2.4 mEq/L	< 2.0 mEq/L
Phlebitis	erythema \geq 2 cm diameter at IV site without swelling, venous cord or fever	erythema and induration \geq 2 cm diameter at IV site without venous cord or fever	erythema and induration \geq 2 cm diameter at IV site with venous cord or fever \geq 38°C	erythema and induration \geq 2 cm diameter at IV site with venous cord and fever \geq 38°C
Pneumothorax	NA	small pneumothorax with no cardiovascular effect -no intervention required	small pneumothorax requiring placement on 100% oxygen	pneumothorax with associated cardiovascular compromise requiring needle decompression or placement of chest tube
Pneumomediastinum	NA	simple pneumomediastinum-asymptomatic (No intervention required)	pneumomediastinum with extrathoracic subcutaneous emphysema (no intervention required)	pneumomediastinum with associated cardiovascular compromise requiring placement of drain or surgical intervention
Subglottic stenosis	Need for racemic epinephrine(X 1 dose)use post-extubation	Need for use of multiple doses of racemic epinephrine	Need for reintubation secondary to respiratory difficulty	Need for surgical resection of subglottic stenosis and/or tracheostomy secondary to sub glottic stenosis
Respiratory nosocomial infection	Post-admit pneumonitis on CXR and phys exam with O2 sat of \geq 90% on room air	Post-admit pneumonitis on CXR and phys. Exam with O2 sat of < 90% on RA, O2 sat \geq 90% on supplemental 02	Post-admit pneumonitis on CXR and phys. exam after admission with O2 sat < 90% on room air, O2 sat 70-90% with supplemental 02	Post-admit pneumonitis on CXR and phys exam with O2 sat of < 90% on room air, O2 sat < 70% with supplemental 02
Hypotension		Reduction of resting mean arterial blood pressure 25-49% of pre-intubation mean arterial pressure	Reduction of resting mean arterial blood pressure 50-74% of pre-intubation mean arterial pressure	Reduction of resting mean arterial blood pressure >75% of pre-intubation mean arterial pressure
Endotracheal tube obstruction	Binary (present or absent)			
Inadvertent endotracheal tube dislodgment				

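### Rebound cerebral edema is a named risk of stopping hypertonic saline, but it is missing from the expected-event list and grading table, and the SAE rules conflict on a death from it

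*Combined protocol and SAP*

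**What the plan says.** All references are to the combined protocol and SAP.

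- **Section 2.4.1.2** gives three known side effects of HPS: hypernatremia, hypokalemia and "Rebound cerebral edema upon termination of therapy".
- **Section 9.2.1** says of the adverse events to be collected: "These will include AE known to be related to the study interventions and pre-specified in 2.4.1.2". On serious events it says: "Only events meeting leading to death, hospitalization or prolongation of hospitalization that are outlined in section 2.4.1.2, or that were unanticipated". A further condition is that the event be considered possibly related to the intervention.
- **Section 9.2.1.3**, under "Potentially attributable to the hypertonic saline intervention", lists hypernatremia, hypokalemia, hyperkalemia and phlebitis. It adds: "Adverse Event grading tables (attached as Appendix B) will be used to define these conditions". The same paragraph promises that the listed events will be tabulated, sent monthly to the local independent safety monitor (ISM), and presented annually to the DSMB and both IRBs. It also promises capture throughout the ward stay, whether or not treatment continues.
- **The table headed "Appendix B - Adverse Event Table"** has no row for rebound edema or raised intracranial pressure.
- **Section 9.2.3** names Section 2.4.1.2 events as reportable, in a sentence that also asks that the event not be due to the malaria.
- **Section 9.2.3.1** says deaths not due to the malaria will be reported. Its first protocol-defined SAE is: "Death not caused by respiratory arrest secondary to intracranial hypertension".
- **Section 2.2.2.4.3**, in the background, finds no data that clearly tie HPS to acute renal failure "or to rebound increases in ICP in humans".

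**The concern.** Of the three HPS risks the protocol names, the one left out of the monitoring list is the one that looks like the disease under study. High sodium or low potassium is a laboratory value. Rebound swelling after HPS stops would appear as returning coma or respiratory arrest in a child admitted with malarial brain swelling. Without a definition, the study clinician has to decide case by case which of the two it was, in a trial where Section 5.3.2 says treatment is not masked.

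Secondary objective 3, the safety of HPS, is at stake. So are two processes that depend on how an event is labelled: submission to the sponsor's pharmacovigilance group (Section 9.3.1) and the halting rule for related SAEs (Section 9.5).

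**Working it through.** The plan states no figure to reproduce here. The check sets the event lists side by side and then follows one hypothetical event through the reporting rules.

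**1. The lists**

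| Event | 2.4.1.2 | 9.2.1.3 | Appendix B |
|---|---|---|---|
| Hypernatremia | yes | yes | yes |
| Hypokalemia | yes | yes | yes |
| Rebound cerebral edema | yes | no | no |
| Hyperkalemia | no | yes | yes |
| Phlebitis | no | yes | yes |

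Two of the three risks in Section 2.4.1.2 carry over, and rebound edema is the one dropped. All four HPS events in Section 9.2.1.3 have an Appendix B row.

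**2. What the omission removes.** Section 9.2.1.3 attaches three things to its listed events: definition through Appendix B, the monthly and annual tabulations, and capture after treatment has ended. Rebound edema falls outside all three. The third matters most, because this event can arise only once HPS stops.

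**3. A fatal case under the SAE rules.** Suppose a child improves, HPS is withdrawn, the brain swells again, and the child dies after a respiratory arrest.
- *Section 9.2.1:* the event is outlined in Section 2.4.1.2 and led to death, so it is an SAE if considered possibly related.
- *Section 9.2.3:* it is reportable as a Section 2.4.1.2 event, but the same sentence asks that it not be due to the malaria. It is unclear how these conditions combine.
- *Section 9.2.3.1, text on deaths:* it is reported if not attributed to malaria.
- *Section 9.2.3.1, first bullet:* it is not a protocol-defined SAE, because the death followed respiratory arrest from raised intracranial pressure. The bullet makes no exception for an HPS cause. Section 2.1.13 gives this same mechanism as the apparent final cause of death in the disease.

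The same death is thus an SAE under one section and outside the protocol-defined list under another.

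**4. What depends on the answer.** Section 9.3.1 sends to the sponsor's pharmacovigilance group those events that meet a protocol-defined serious criterion. Section 9.5 suspends enrollment pending a safety review after any SAE deemed related to an experimental intervention. Section 4 has the ISM comment on relatedness for SAEs. Each step presupposes the classification that step 3 leaves open.

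**5. What is observed after HPS stops.** Sections 2.2 and 4 withdraw HPS once the brain volume score is 5 or less and the Blantyre Coma Score is at least 3. Section 4 schedules daily MRI only while the child is unconscious, and Appendix A applies that condition from Day 2. Routine imaging may therefore not cover the period after withdrawal. Coma scoring continues, and Section 8.1 schedules transcranial Doppler every 24 hours during the hospital stay.

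**The case against.** The strongest reply is that rebound edema is already inside the safety system.

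- **Collection.** Section 9.2.1 brings in Section 2.4.1.2 events by cross-reference and adds that all adverse events on study are documented whatever their relationship. The Section 9.2.1.3 list marks events of special concern and is not the limit of collection.
- **Grading.** Section 9.2.1.1 has a generic severity scale for events outside the tables. Lack of a row is not unique to this event: stridor, bronchospasm and pulmonary hemorrhage are expected ventilation events and also have no row of their own in the extracted table.
- **Deaths.** Survival by arm is the primary safety parameter (Section 9.1), and the DSMB reviews safety and efficacy by arm (Section 9.6). Death or rescue ventilation within 7 days in the HPS arm is treatment failure on the primary outcome.
- **Imaging.** A child who lapses back into coma again meets the condition for daily MRI, if stable for transport.

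Most of this stands. A reader might infer from the first bullet of Section 9.2.3.1 that a death from rebound edema is exempt from SAE reporting, or that HPS safety cannot be assessed for this event. The documents support neither reading. Sections 9.2.1 and 9.2.3 and the text on deaths in Section 9.2.3.1 all provide a reporting route, and deaths are counted by arm whatever their label.

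The reply does not remove the gap. The reporting routes depend on an unmasked judgment of cause with no definition to guide it. A severity scale grades an event once it is recognised but does not say what the event is. Survival by arm nets any benefit of HPS against any harm, so it cannot isolate rebound. In addition, 48 of the 64 usual-care children in Section 11.5 are historical controls.

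**Conclusion.** The point holds as an inconsistency with consequences for safety monitoring. One of three named HPS risks has no event-specific definition or grade and is outside the special-concern tabulations and the post-treatment capture sentence. Sections 9.2.1 and 9.2.3 conflict with the first bullet of Section 9.2.3.1 on whether a death from it is a reportable SAE, and Sections 9.3.1 and 9.5 inherit that ambiguity. HPS safety assessment is weakened but remains possible.

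The defect has no numerical size. The projected HPS arm is 32 children, but a zero-event confidence bound on 32 would describe the precision of any arm that large, not this gap. Children who die while still on HPS also never reach withdrawal. The primary analysis is not affected.

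The conclusion assumes that the extracted Appendix B is complete for HPS events. It also assumes that fatal rebound edema would act through raised intracranial pressure and respiratory arrest, as the protocol's own hypothesis suggests for malarial swelling. Whether HPS causes rebound in humans is not settled here: Sections 2.2.2.4.3 and 2.4.1.2 read differently, and the cited sources were not available.

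**What to change.** 1. Add rebound cerebral edema to the HPS list in Section 9.2.1.3 and give it a row in Appendix B. The sponsor should set the definition and the time window, using observations already collected, such as coma score, respiratory arrest, transcranial Doppler and any repeat MRI.
2. Reconcile Sections 9.2.1, 9.2.3 and 9.2.3.1 so that every death after HPS has stopped reaches the ISM and the DSMB for a relatedness review, without first depending on the site's attribution to malaria or to rebound.
3. Reconcile Section 2.2.2.4.3 with Section 2.4.1.2, without presuming which is right.

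A definition tied to stopping HPS describes the HPS arm only. Its rate should not be presented as a between-arm comparison unless the same observations are summarised over a comparable period in the other arms.

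The cost is protocol wording, one eCRF field and a few more SAE reports. Some of those reports, if deemed related, could trigger the enrollment suspension and safety review in Section 9.5. No new procedure or change to treatment is needed.
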